#### 13.12. Definition of study population

#### 13.12.1. General Issues

Before the study is unblinded, a blind review will be performed. In this process, possible protocol violations will be classified as "severe", "major", "minor", or "none". Patients will be allocated to the individual data sets with regard to the classification of

possible protocol violations. The analysis populations (Safety, ITT, and PP) will be listed individually in the final statistical analysis plan.

#### 13.12.2. Safety Population

Safety population includes all patients who have had at least one dose of study medication and one contact with the Investigator afterwards. It will be used for safety analysis.

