#### 7.5. Treatment Compliance

Since the infusion will be administered by a nurse or physician, documentation of the infusion procedure in the rating book will serve as the basis for compliance assessment.

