#### An Adverse Drug Reaction is considered serious if it:

- Results in Death
- Is life threatening
- Requires additional inpatient hospitalization or prolongation of existing hospitalization
- Results in persistent or significant disability / incapacity
- Results in a congenital anomaly or birth defect

• Other medically significant event that requires immediate medical or surgical intervention

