#### 10.5. Recording of Adverse Events

All adverse events occurring after the start of the study must be reported, according to previously provided definitions, whether they are considered serious or not and regardless of the relationship to teh strudy medication will be documented in the CRF and were applicable reported. Subject entry into the study is defined as the time the informed consent is signed.

The nature of each individual AE, date and time of onset, duration, severity, relationship, any actions taken as well as outcome must be documented by the investigator. Additionally, it will be recorded whether the AE was serious nor not. Details of change to the dosing schedule or any corrective treatment must be recorded on the appropriate pages of the CRF.

The investigator is obliged to follow-up patients with AEs until the event has subsided, the condition is considered medically stable, or the patient is no longer available to follow-up. Patients who discontinue the study drug due to adverse experiences (clinical or laboratory) will be treated and followed according to established acceptable medical practice - all pertinent information concerning the outcome of such treatment will be entered on the CRF. AEs already documented in the CRF at a previous visit and designated as continuing must be reviewed at each visit. If an AE is resolved, documentation in the CRF must be completed to that effect. If an AE changes in frequency or severity during a study period, a NEW record of that experience will be initiated.

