#### 13.11. Accounting for missing data

#### 13.11.1. Missing Data Problems – General Considerations

Missing data are a problem in every data analysis. Of course, there are always missing data of the type 'missing completely at random' (MCAR), which in principle will not bias the results; the analysis procedure should be able to cope with partially missing data of such a type. In many studies this type of data is treated by LOCF replacement (Last Observation Carried Forward) as far as there exist follow-up measurements at previous visits.

In a study like the one planned there might also be informatively missing data (missing not at random, MNAR): participants of the study died or are unable to complete the tests because of brain-related impairment. Neglecting these missing data might introduce bias.

A reasonable policy for minimizing bias in the case of informatively missing data (MNAR) is the replacement of these missing data by assigning the worst possible score, or a score worse than those observed. It should be noted that this strategy is only reasonable if rank-based robust procedures are used for the data analysis.

The worst rank imputation procedure was recommended by Lachin in his seminal paper about the missing data problem for data missing because of mortality when performing an exercise test (Lachin, 1999). This procedure was also used when analyzing non-fatal outcomes in studies where mortality was a problem (Lusben, 2002; McMahon, 2001). Recently a similar procedure has been proposed by the 'Traumatic Brain Injury (TBI) Clinical Trials Network' when designing the COBRIT study (Bagiella, 2010).

Temkin (2007) included deaths with the worst rank for the significance tests of neuropsychological scales but excluded deaths for the calculation of descriptive statistics (e.g., mean, SE estimates). Thus, significance tests reflect all patients with estimation of missing data while the descriptive statistics reflect only the actually observed assessments. We prefer not excluding deaths from descriptive statistics, since the study treatment with more deaths would artificially have better neuropsychological scores while a study treatment preventing deaths would be burdened by rather severe scores of survived patients. The use of robust descriptive statistics in this study allows the inclusion of worst rank scores for deaths also in

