#### 13.12.3. Full Analysis Set (FAS)

FAS population is defined as all patients who have no "severe" violation of entry criteria, had at least one dose of medication and at least one post-baseline observation of at least one primary efficacy criterion (definition according to ICH E9 § 5.2. Analysis Sets). FAS population will be used for all efficacy analyses.

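### The safety population requires an Investigator contact after dosing, so a patient who dies or is lost after the first infusion(s) and before any such contact is left out of the safety analysis

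*Protocol*

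**What the plan says.** Protocol section 13.12.2 defines the set in one sentence: "Safety population includes all patients who have had at least one dose of study medication and one contact with the Investigator afterwards". Its purpose follows: "It will be used for safety analysis". Section 13.12 names no other set for safety. Nothing there exempts deaths or serious events from the contact condition, and contact is not defined.

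Three other parts of the protocol bear on the point:

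- **Who gives the infusion.** Section 7.5 bases compliance on the infusion record: "Since the infusion will be administered by a nurse or physician". The person present at an infusion may therefore be a nurse.
- **What must be recorded.** Section 10.5: "All adverse events occurring after the start of the study must be reported". The same section fixes when that duty begins: "Subject entry into the study is defined as the time the informed consent is signed". Neither sentence sets a contact condition.
- **How deaths are treated in the efficacy data.** Section 13.11.1: "We prefer not excluding deaths from descriptive statistics, since the study treatment with more deaths would artificially have better neuropsychological scores".

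Sections 13.12.1 and 13.15 leave to the SAP the individual listing of the populations. The definition itself is fixed in the protocol.

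**The concern.** A safety set is normally everyone exposed to treatment. Here a treated patient can be removed by something that happens, or fails to happen, after the dose. The patients who can fail the contact condition are those who die or disappear early. An early death is among the events that a safety analysis most needs to count.

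Drug safety is a stated secondary objective (section 4.2). Under sections 10.2.1 and 10.6, reporting to the Coordinator within 24 hours is tied to a suspected causal relationship, and other serious events go to adverse event documentation. For a death judged unrelated, the comparison between arms is therefore the main place where an imbalance could show. A rule that can drop such a death weakens that comparison, and the losses need not be equal in the two arms.

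**Working it through.** The protocol gives no figure to reproduce here, so the check is mainly textual. A short illustration of size follows.

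**Step 1: apply the definition.** Take a patient who is randomised, has the first infusion from a nurse, and dies or is lost before any contact with the Investigator.

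- Condition 1, at least one dose: met.
- Condition 2, a later contact with the Investigator: not met.
- Result: outside the safety population.

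**Step 2: compare with the recording rule.** Section 10.5 counts the patient as in the study from consent and requires the event to be documented. The event is in the CRF, but the patient is not in the set analysed.

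**Step 3: look for another route into the analysis.** The full analysis set (section 13.12.3) does not help. Apart from the entry-criteria condition, it requires that the patient "had at least one dose of medication and at least one post-baseline observation of at least one primary efficacy criterion", which someone who died or left this early cannot supply. The per-protocol set is a subset of the full analysis set.

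**Step 4: find how long a patient is exposed to the rule.** One qualifying contact is enough. The window runs from the first infusion to the first later Investigator contact and then closes for the rest of the 40 planned infusions (4 cycles × 10). Cycle 1 is daily on days 1 to 10 with adverse event monitoring (section 11.1), so the window is probably hours or days. Section 11.1 does not say who does that monitoring, and the next scheduled evaluation visit after baseline is day 180. The length therefore depends on how contact is read.

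**Step 5: compare with the protocol's own reasoning.** Section 13.11.1 keeps deaths in the efficacy data because leaving them out flatters the arm with more deaths. Section 13.12.2 does not apply that reasoning to safety.

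**Step 6: illustrate the size.** Inputs: 145 patients planned per arm (section 13.8), all assumed dosed. The numbers of deaths are assumed, since the protocol gives none. With D deaths in an arm and k of them excluded, the rate changes from D/145 to (D − k)/(145 − k).

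| Deaths D | All treated | k = 1 excluded | k = 2 excluded |
|---|---|---|---|
| 3 | 3/145 = 2.1% | 2/144 = 1.4% | 1/143 = 0.7% |
| 5 | 5/145 = 3.4% | 4/144 = 2.8% | 3/143 = 2.1% |
| 10 | 10/145 = 6.9% | 9/144 = 6.3% | 8/143 = 5.6% |

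One death is 1/145 = 0.69 percentage points of an arm's mortality.

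Excluding a patient lost without a known event acts the other way and is much smaller. With 3 deaths, 3/145 = 2.07% becomes 3/144 = 2.08%.

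**The case against.** The case for leaving the text alone is that the rule will rarely matter. Infusions in cycle 1 are daily with adverse event monitoring. Section 10.5 has the Investigator document and follow each event, so a surviving patient with a reaction would ordinarily meet the contact condition. Section 6.6.2 asks for reasonable effort to reach patients lost to follow-up. Contact is not limited to scheduled visits, and section 7.5 names a physician as well as a nurse. All of this stands, and it confines the realistic gap to a death or complete loss soon after the first dose(s). It does not close the gap.

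Two stronger readings are tempting, and the protocol supports neither:

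- **That a death after any infusion would be dropped.** A reader might infer this from the definition. It is not so: any earlier post-dose contact keeps the patient in, so deaths around later infusions are normally counted.
- **That the rule hides harm and biases the comparison towards no harm.** The event must still be in the CRF, so it is omitted from the analysis set but not concealed. The direction is also open. An excluded death on Cerebrolysin would favour Cerebrolysin, an excluded death on placebo would do the reverse, and an excluded loss without an event slightly raises that arm's rate.

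There is also a fair objection to an all-treated set: patients with no post-dose information then count as event-free and dilute the rate. That is true, and the fix allows for it.

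**Conclusion.** The point holds as a narrow flaw in a definition that the protocol fixes. Membership of the safety population depends on a post-randomisation event, and on the literal wording an early death after the first infusion(s) can be left out of the safety analysis although it must be recorded.

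The number affected is likely to be small, and the protocol gives no basis for estimating it. For scale, one death is 0.7 percentage points in an arm of 145. The changes in rates shown above rest on assumed death counts and on all 145 patients being dosed. The direction of any bias cannot be stated in advance.

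The conclusion rests on two readings: that the two conditions are joint, as written, and that an infusion given by a nurse is not in itself a contact with the Investigator. If contact were read to include any attendance with study staff, the window would shrink, but a death or loss directly after the first dose would still be excluded. No sample size, power or alpha figure is affected. This is a minor point, worth correcting because the correction is so cheap.

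**What to change.** In section 13.12.2, delete the condition on Investigator contact after dosing, so that the safety population is all patients who received any study medication. Carry the same definition into the SAP.

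Report, by arm, the number of treated patients with no post-dose information. They enter the denominator as event-free, which slightly dilutes event rates, and the count lets a reader judge how much.

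The cost is one deleted phrase and one extra line in the safety tables. Because populations are assigned at the blind review, the change should be documented before unblinding. It involves no new data collection and no change to clinical conduct.

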#### 13.12.3. Full Analysis Set (FAS)

FAS population is defined as all patients who have no "severe" violation of entry criteria, had at least one dose of medication and at least one post-baseline observation of at least one primary efficacy criterion (definition according to ICH E9 § 5.2. Analysis Sets). FAS population will be used for all efficacy analyses.

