#### 4. STUDY OBJECTIVES

This study shall assess the efficacy of pharmacological intervention with Cerebrolysin in the prevention of post stroke cognitive decline.

The aim of this trial is to test the hypothesis that patients randomized to Cerebrolysin show improved cognitive outcome measured with a battery of co-primary neuropsychological tests as compared to patients randomized to placebo (multivariate analysis of combined cognitive outcome measures).

Furthermore, it is intended to investigate the hypothesis that Cerebrolysin, as compared to placebo, will show improved scores at four, seven and thirdteen months post-stroke on neurological deficit, global function, depression and anxiety. In addition, it is intended to investigate the effects of Cerebrolysin versus Placebo on the Quality of Live at seven and thirdteen months after stroke. Furthermore, it is intended to evaluate the safety of Cerebrolysin in patients with recent stroke and to determine which demographic, clinical and radiological characteristics predict response to treatment with Cerebrolysin.

Other study designs, including non-randomised controlled trials, can detect associations between an intervention and an outcome. But they cannot rule out the possibility that the association was caused by a third factor linked to both intervention and outcome. Random allocation ensures no systematic differences between intervention groups in factors, known and unknown, that may affect outcome. Double blinding ensures that the preconceived views of subjects and clinicians cannot systematically bias the assessment of outcomes. Intention to treat analysis maintains the advantages of random allocation, which may be lost if subjects are excluded from analysis through, for example, withdrawal or failure to comply. Meta-analysis of controlled trials shows that failure to conceal random allocation and the absence of double blinding yield exaggerated estimates of treatment effects.

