#### 11. STUDY SCHEDULE

#### 11.1. **Procedures at Each Visit**

#### Visit 1 – Screening PART 1 - within 72h after onset of the stroke (Study Day -30)

Visit 1 will be perfomed 30  $\pm$  3 working days prior to randomization and the baseline assessment

- In/exclusion criteria PART 1
  - CT
  - NIH Stroke Scale score between 5-15 at inpatient admission
  - IQ Code
- Demographic data
- Medical history
- Concomittant Medication

#### Run-In Period – Study Day -30 to Study Day 1

The Run-In period shall continue for 25 to 30 days beginning visit one. During the Run-In period the following will be performed

- MRI will be performed before study baseline
- Monitoring of concomitant medication
- Standard stroke treatment

#### Visit 2 – Screening PART 2 & Baseline Assessment – Study Day 1

- Informed Consent (signed up to Visit 2 start)
- In/exclusion criteria PART 2
  - Mini-Mental State Examination (MMSE)
  - Goodglass & Kaplan Score
- Randomization
- Primary Evaluation Scales Baseline Assessment
  - Stroop Color Word test (Stroop)
  - Trail-Making-Test Part A (TMT-A)
  - Digit Span Backward Task (DS-BW)
  - Digit Symbol (DS-WPSI)
  - Verbal Fluency Test CFL Version (VFT-CFL)
  - Rey Auditory Verbal Learning Test (RAVLT)
- Secondary Evaluation Scales Baseline Assessment
  - Montreal Cognitive Assessment (MOCA)

- Modified Rankin Scale
- NIH Stroke Score
- Hospital Anxiety and Depression Scale
- EQ-5D-5L
- Drug Safety Parameters
  - Adverse Events
- Concomittant Medication Monitoring

#### Treatment Cycle 1 – Study Day 1 to 10

During the first treatment cycle each patient shall receive 10 infusions, once daily on 10 consecutive days. The first infusion will be given after all baseline assessments have been performed. The following procedures will be performed during treatment visits:

- Adverse Event Monitoring
- Concomittant Medication Monitoring

## Treatment Cycle 2 – Study Day 61 to 70

During the second treatment cycle each patient shall receive 10 infusions, once daily on 10 consecutive days. The following procedures will be performed during treatment visits:

- Adverse Event Monitoring
- Concomittant Medication Monitoring

#### Treatment Cycle 3 – Study Day 121 to 130

During the second treatment cycle each patient shall receive 10 infusions, once daily on 10 consecutive days. The last infusion will be given on the day of Visit 3 before the assessments The following procedures will be performed during treatment visits:

- Adverse Event Monitoring

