- Concomittant Medication Monitoring

#### Visit 3 – Efficacy & Safety Assessment – Study Day 180

- Primary Evaluation Scales Baseline Assessment
  - Stroop Color Word test (Stroop)
  - Trail-Making-Test Part A (TMT-A)
  - Digit Span Backward Task (DS-BW)
  - Digit Symbol (DS-WPSI)
  - Verbal Fluency Test CFL Version (VFT-CFL)
  - Rey Auditory Verbal Learning Test (RAVLT)

- Secondary Evaluation Scales Baseline Assessment
  - Montreal Cognitive Assessment (MOCA)
  - Modified Rankin Scale
  - NIH Stroke Score
  - Hospital Anxiety and Depression Scale
  - EQ-5D-5L
- Drug Safety Parameters
  - Adverse Events
- Concomittant Medication Monitoring

#### Treatment Cycle 4 – Study Day 241 to 250

During the second treatment cycle each patient shall receive 10 infusions, once daily on 10 consecutive days. The following procedures will be performed during treatment visits:

- Adverse Event Monitoring
- Concomittant Medication Monitoring

#### Visit 4 – Efficacy & Safety Assessment – Study Day 360

- Primary Evaluation Scales Baseline Assessment
  - Stroop Color Word test (Stroop)
  - Trail-Making-Test Part A (TMT-A)
  - Digit Span Backward Task (DS-BW)
  - Digit Symbol (DS-WPSI)
  - Verbal Fluency Test CFL Version (VFT-CFL)
  - Rey Auditory Verbal Learning Test (RAVLT)
- Secondary Evaluation Scales Baseline Assessment
  - Montreal Cognitive Assessment (MOCA)
  - Modified Rankin Scale
  - NIH Stroke Score
  - Hospital Anxiety and Depression Scale
  - EQ-5D-5L
- Drug Safety Parameters
  - Adverse Events
- Concomittant Medication Monitoring

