ordinal/rating scales it is regarded as method of choice or 'gold standard', see also Design and Analysis of Non-Inferiority Trials (Rothmanns et al. 2011).

Technically, the MW gives the probability that a randomly chosen patient of the test group is better off than a randomly chosen patient of the comparison group (with the probability ranging from 0 to 1, with 0.5 indicating equality); it is statistically defined as: P(X < Y) + 0.5 P(X = Y).

Applying the Mann-Whitney effects size measure, the null and alternative hypothesis for the comparisons of the test treatment to control treatment (superiority) can be formulated as follows:

The traditional benchmarks for the Mann-Whitney effects size measure (MW) are as follows (Colditz,1988):

- 0.29 large inferiority
- 0.36 medium inferiority
- 0.44 small inferiority
- 0.50 equality
- 0.56 small superiority
- 0.64 medium superiority
- 0.71 large superiority

The confirmatory analyses are performed with the FAS population according to the ICH Guideline E9 (full analysis set). Since the use of the per protocol set, however, maximises the opportunity for a new treatment concept to show additional efficacy in the analysis, and most closely reflects the scientific model underlying the protocol (see ICH E9, section 5.2.2), the supportive analysis by means of the per-protocol set will be regarded as of equal scientific importance (see also Schwartz 1967, Schwartz 1980, Senn 2007).

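### The FAS definition shuts out every treated patient who dies before day 180, although section 13.11 means to keep deaths in with the worst rank

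*Protocol*

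**What the plan says.** Section 13.12.3 sets three conditions for the FAS. The patient must have no severe violation of entry criteria, and must have "had at least one dose of medication and at least one post-baseline observation of at least one primary efficacy criterion". The same section states that the "FAS population will be used for all efficacy analyses", and section 13.9 names the FAS as the set for the confirmatory tests. The per-protocol set in 13.12.4 is drawn from the FAS.

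The primary criteria are six cognitive tests. Section 11.1 schedules them at baseline and then first under "Visit 3 – Efficacy & Safety Assessment – Study Day 180", and once more at day 360. For each treatment cycle before day 180 (days 1-10, 61-70 and 121-130), the list that follows "The following procedures will be performed during treatment visits" contains only adverse events and concomitant medication.

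Section 13.11.1 describes the informatively missing data expected in this trial: "participants of the study died or are unable to complete the tests because of brain-related impairment. Neglecting these missing data might introduce bias". It adopts worst-rank handling and declines to leave deaths out even of descriptive statistics, because the arm with more deaths would look artificially better. Section 13.11.2 codes each scale as 1 (valid), 2 (not completed for a stroke-related neurological reason) or 3 (not completed for another reason). Section 13.11.3 gives code 2 the worst score of the scale.

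**The concern.** Imputation can only reach patients who are in the analysis set. A treated patient who dies before day 180 has no post-baseline cognitive test and leaves the set before the worst-rank rule can act. Membership then depends on an outcome after randomisation that treatment may affect. The first confirmatory test, at day 180, opens the way to the second at day 360 (section 13.7), so the exclusion enters at the first step.

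The effect reaches beyond cognition. Sections 9.2.2 and 9.2.3 assign the worst NIHSS score and an mRS of 6 to patients who die. Because FAS entry depends on a cognitive test and the FAS governs all efficacy analyses, early deaths drop out of those scales too. No defined efficacy set keeps them. Section 13.12.1 mentions an ITT population but does not define it, and 13.15 puts the FAS in its place.

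**Working it through.** **Inputs from the protocol (13.6, 13.8):** 145 per group including 15% for dropouts, two-sided alpha 0.05, power 90%, MW = 0.60 (d = 0.35), correlation 0.6, six outcomes. **Assumed:** early-loss rates of 5% to 15% per arm, since the protocol gives none.

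**1. The plan's own figure.** For an average of six equally correlated outcomes the variance factor is (1 + 5 × 0.6)/6 = 0.667. With d = 0.35 and Wilcoxon efficiency 0.955, n = 171.5 × 0.667/0.955 = 119.8, so 120; 120/0.85 gives 142 per group, within 3% of 145. Noether's formula with MW = 0.60 gives 175.1 × 0.667 = 116.7, so 117, and 117/0.85 gives 138. The stated 145 is not in dispute.

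**2. Who is excluded.**
- Dies before day 180: no test possible, outside the FAS.
- No valid result on any of the six tests at day 180 or day 360: outside the FAS, if a code 2 is not an observation.
- One valid test at either visit: inside the FAS, and worst rank applies to the code-2 scales.
- Tested at day 180, untestable at day 360 for a stroke-related reason: inside the FAS, worst rank at day 360.

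At 145 per arm, losses of 5%, 10% or 15% would remove about 7, 15 or 22 patients per arm (145 × 0.05 = 7.25, and so on).

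**3. Effect on the estimate.** Let pt and pc be the proportions lost on Cerebrolysin and placebo, and MWs the value among testable patients. If lost patients rank last on all six scales, then over all treated patients

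MW = (1 - pt)(1 - pc) × MWs + pc(1 - pt) + 0.5 × pt × pc.

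With MWs = 0.50 this reduces to MW = 0.5 + 0.5(pc - pt). If loss is unrelated to cognition, the FAS as written estimates MWs.

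| pt | pc | FAS as written | All treated, worst rank |
|---|---|---|---|
| 10% | 10% | 0.50 | 0.500 |
| 5% | 10% | 0.50 | 0.525 |
| 10% | 5% | 0.50 | 0.475 |
| 15% | 5% | 0.50 | 0.450 |
| 5% | 5% | 0.60 | 0.590 |
| 10% | 10% | 0.60 | 0.581 |
| 15% | 15% | 0.60 | 0.572 |
| 5% | 10% | 0.60 | 0.611 |
| 10% | 5% | 0.60 | 0.561 |
| 15% | 5% | 0.60 | 0.531 |

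For example, with 10% in both arms and MWs = 0.60: 0.81 × 0.60 + 0.10 × 0.90 + 0.5 × 0.01 = 0.486 + 0.090 + 0.005 = 0.581.

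**4. Effect on power.** This was simulated with 145 per arm, six outcomes, correlation 0.6 and 1,500 runs, with MWs = 0.60.
- Loss of 10% in both arms: about 80% with worst rank, 94% in the FAS.
- Loss of 10% on Cerebrolysin, 5% on placebo: about 58% against 95%.
- Loss of 5% on Cerebrolysin, 10% on placebo: about 97% against 94%.

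**5. Loss related to cognition.** With no treatment effect, losses of 15% on Cerebrolysin and 5% on placebo, and an assumed correlation of 0.5 between loss and cognition, the FAS drifts to about 0.517. It then declares Cerebrolysin superior in about 10% of runs, against a nominal 2.5%. This is the extreme of the range tried.

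**The case against.** A reader might infer that the FAS rule and the worst-rank rule can never operate together. They can. The FAS asks for one observation of one criterion and names no visit, so worst rank still covers partly testable patients, those untestable at day 180 but tested at day 360, and those who become untestable for a stroke-related reason after a day-180 test.

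For wholly untestable patients the exclusion rests on a reading. Section 13.11.2 codes every patient at every visit, and the protocol does not say whether a recorded code 2 is an observation. Given the intent in 13.11.1, a definition could settle this in the patients' favour. It would not settle deaths, which have no code.

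The size is not shown to be realistic. Baseline is about a month after the stroke. Sections 6.2 and 6.5 exclude an MMSE below 12, a Goodglass and Kaplan score below 2, NIHSS item 9 of 2 or more, expected survival under a year and advanced organ disease. These criteria screen out many patients likely to be lost early. This stands, and the rates above are illustrations only.

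Section 4 is weak support for a charge of breach. Its statement, "Intention to treat analysis maintains the advantages of random allocation, which may be lost if subjects are excluded from analysis through, for example, withdrawal", is general text on why trials are randomised and does not define the analysis set.

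A reader might also look for an earlier test. Section 5 announces five visits but describes four, sections 4 and 13.7 mention month 4, and the cycle 3 text in 11.1 places its last infusion on the day of Visit 3. These passages need reconciling, but none schedules a cognitive test between baseline and Visit 3.

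Finally, the FAS and population listings go into a final SAP that is not shown. But the protocol already fixes the FAS definition, and an SAP that follows it carries the conflict forward.

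**Conclusion.** The conflict is real and clear for deaths before day 180. The text excludes them from all efficacy analyses, while 13.11.1 intends to keep deaths. It is probable, but open to definition, for patients with no valid result on any test at either visit. It does not extend to other patients.

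The size is unknown. With no effect in testable patients, assumed losses of 10% and 5% should shift MW by 0.025 in either direction, a quarter of the planned 0.10, and the FAS shows none of it. The table assumes that lost patients rank last on all six scales and that loss is otherwise unrelated to cognition.

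It would be tempting to say that the rule favours Cerebrolysin or inflates the type I error. The documents do not support either as a general statement. The direction depends on which arm loses more patients. Equal loss leaves the null value at 0.50, although it removes the penalty that worst rank was meant to apply. The roughly 10% false-positive rate needs both unequal loss and loss related to cognition.

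**What to change.** 1. **13.12.3:** define the FAS as all randomised patients with at least one dose and no severe entry violation judged on pre-treatment data, and delete the observed-test condition. Alternatively, keep the condition and state that death or a code 2 satisfies it.
2. **13.11.2:** add an explicit code for death. Repairing 13.12.3 alone is not enough: a death unrelated to stroke could be given code 3, and 13.11.4 leaves day 180 missing when no earlier follow-up exists.
3. **13.11.3:** give death the worst score at all visits after death. Give a code 2 the worst score only at the visit where it is recorded, and use a later valid test as observed. Carrying the worst score forward would overwrite a valid day-360 result.

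The SAP should repeat the three changes, and they should be settled before unblinding.

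The cost is short edits to three sections and no new data. The statistical cost can be material and should be accepted knowingly. MW and power may fall even when losses are equal (0.60 to 0.581, and about 94% to 80% power, at an assumed 10% in both arms). They may rise if fewer patients are lost on Cerebrolysin (0.611 at 5% against 10%).
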